**Table 4: Example Findings from Qualitative Analyses of Staff Interviews**

	Sites (in order from least to biggest decrease in HbA1c)			
	1	2	3	4
A	-2	+	0	+
B	+	+	0	+
C	-1	-2	0	+
D	-2	0	+	+

Aim 4 (Obtain data throughout implementation on the staff effort required, to be used for calculating the costs of the program): Costs will be assessed from the VA perspective and will focus on the direct costs of the P2P program itself. We will ask the facilitators to record the number of group visits and duration of each, and the time spent in training and pre-visit preparation.

### 5.6.2 Sample Size and Power Calculations

We chose five VA health systems (8 sites, as one healthy system will implement the program in 4 separate sites within the system) in which to implement SMAs + P2P based on our estimation of feasibility of implementation, given budget and time constraints. This number of health systems should also provide some variability in terms of the CFIR constructs (especially implementation context), which is important for investigating the role of these constructs in implementation success. We want to ensure that the study has a sample size sufficient to detect a clinically meaningful decline in A1c of 0.5% or a SBP decline of 5mm Hg between SMA and SMA+P2P. Based on discussions with clinical managers at a number of sites, both in relation to this project and others, they would be unlikely to undertake an addition of a new clinical management strategy unless it offered a benefit of this magnitude.

The clustering induced by the treatment in small groups requires that we account for the intra-class correlation within clusters in our sample size calculation. An increasing number of publications have started to provide estimates of ICCs from practice-based interventions. However, there are not good sources for estimates of ICCs of clinical intermediate outcomes induced by shared medical appointments. In a previous RCT conducted by us of P2P alone, which given the intimate nature of the pairing may represent an upper limit of induced correlation that might be found in a larger SMA, we found that the ICC was estimated at 0.10 but it was not significantly different from 0. Thus we used a range of 0 to 0.10 for the estimate of ICC of the outcome a1c or SBP measurement.

We present sample size calculations using Satterthwaite's approximate F test using modified degrees of freedom rather than a t-test to calculate the power for trials and the number of clusters and cluster sizes required for the difference of means in the presence of clustering or differential clustering effects between study arms as described by Roberts (2005) and implemented by Batistatou and Roberts (2011). We estimate that we can conduct 10 to 16 SMA groups per site (equally distributed between SMA and SMA+P2P) with 8-14 people per group. At our low estimate of 10 SMA groups per site, we can detect an effect size of 0.5% decline in A1c with a power of 0.8 for all but the lowest number of participants per group (10) and highest ICC (0.1).

For the comparison of both SMA groups to inactive control we must take into account the differential ICC between groups as the inactive controls will have no clustering induced by the treatment and therefore will have an ICC of 0. We continue to assume a worst case scenario of an ICC of 0.10 in the intervention group. In this case we examine our ability to detect a difference of 5mm Hg in blood pressure between SMA groups and the inactive controls.

The standard deviation of a decline in A1c was estimated to be 1.45 from this same RCT mentioned in the paragraph above. The estimate of the standard error of the change in BP was estimated from a database of actual BPs obtained in routine clinical practice for 24,000 patients with diabetes and hypertension in one large service network in the VA over a 24 month period in FY 2004-2005. It depends on both the variation in BP change at the person level and variability within person between measurements. Increasing numbers of measurements in the 6 month window decreases the within person component of variance. Using the proposed 6 month pre- and post-intervention windows on either side of a 12-month intervention period we estimated the standard error for the change in blood pressure as 17 mmHg for the mean of 3 BP measurements that was observed in the sample for each of the pre and post periods.

Again, we assume that we can conduct 10 to 16 SMA groups per site (equally distributed between SMA and SMA+P2P) with 8-14 people per group. At the maximum, this would give us 1,568 people in active treatment and an equal number of inactive controls. At the minimum, this would give us 560 people in active treatment and an equal number of inactive controls. In this scenario, at our low estimate of 10 SMA groups per site, we can detect an effect size of 5mm decline in SBP with a power of 0.8 across all our ranges of group size and ICC. In this scenario, we also have a power at 0.8 at all estimated ICCs to detect a 0.5% difference in A1c between the active treatment groups and controls.

Table 5 shows a snapshot of the number of eligible patients per site. Across all sites, we will recruit between 560 and 1,568 active treatment patients and an equal number of inactive controls.

**Table 5: Number of Patients with Diabetes\* with qualifying A1c\*\*, and Number of These Patients with and without Serious Mental Illness (SMI) or Substance Use Disorder (SUD) and with SBP>140**

Site	No. of Diabetes Patients	No. of Diabetes Patients without SMI or SUD	No. of Diabetes Patients with Qualifying A1c**	No. with Mean SBP>140 in Past 6 months
West Haven (Firm A)	3,748	306	397	187
Providence	5,466	636	794	105
Palo Alto	3,877	404	534	110
Livermore	1,212	156	168	88
Monterey	3,736	298	381	160
Sacramento	5,847	858	1,045	210
Ann Arbor	11,020	2,064	2,576	955

\*Source: VHA CWD (last updated 2015).

\*\*Patients less than 70 years old with A1c>7.5, for patients age 70 or above Ac1>8.0

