### 5.0 Study Procedures

#### 5.1 Study Design

##### 5.1.1 Overview

This study represents Steps 4 and 5/6 of the QUERI Process, which are also described under "Implementation Trial with Evaluation" in the new Research/Implementation Pipeline used for the most recent QUERI Annual Reports (Appendix 1 to this protocol). Specifically, this will be a hybrid 1 effectiveness trial conducted under real-world implementation conditions in multiple sites and regions. The focus is on assessing the impacts of the program on patient outcomes (research aims 1-2), as well as optimization of the implementation strategy (aim 3).

This project is being conducted at five VA facilities (including eight clinics) implementing SMAs as part of usual care. These sites have been selected because they are interested in implementing P2P groups as an add-on to the SMAs as part of usual care. As these programs are starting, resources at each site do not permit all eligible patients to receive these two new programs. Therefore there are three groups being studied, all receiving usual care for their facilities: (1) usual care without SMAs, (2) usual care with SMAs, and (3) usual care with SMAs and P2P.

The study design is a multi-site, modified cluster randomized controlled design. Our first analysis is a comparison of two active treatment arms, one involving SMA and the second involving SMA+P2P. Some sites may only conduct one group at a time depending on variability of their resources over time, but all sites will conduct a number of groups over the study period and the two

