#### **Data Pull**

Each quarter, the Data Manager will pull a list of all patients meeting the eligibility criteria outlined below. At our Ann Arbor site and Palo Alto site and subsites, the RC will provide

each newly eligible patient's assigned provider (PCP or RN) the opportunity to opt that patient out of SMA recruitment. Providers will be asked to respond within 1 week and at that point, any patients who were not opted-out will be recruited.

Eligible patients will be sent an SMA Info Letter explaining that they are being invited to participate in SMAs, provided a brief description of what the SMAs involve, and informed that some groups will also be offered an additional (optional) opportunity to participate in P2P as a supplement to the SMAs. This introductory letter will also explain that they will be asked if they are interested in participating in a research study to evaluate this program. It will explain that they may participate in the SMAs regardless of their decision to participate in the research study. It will also include a phone number to call to opt-out of the invitation to participate in the research study, or to opt-out of both the invitation to participate in SMAs and the research study. Unless patients respond that they do not wish to participate, the letters will be followed with a phone call to further describe the program. If patients are interested in participating, they will also be asked a set of brief screening questions to screen out people with active substance abuse. Then the RC will schedule the patient to attend an upcoming SMA or SMA + P2P meeting. Veterans who do not wish to participate will be replaced with another Veteran randomly selected from the population of eligible Veterans, until the SMA group is filled. A full group will range from 10 – 14 patients depending upon the site resources.

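### Section 5.6.2 mixes three site counts and two minimum group sizes, so its A1c power statement for SMA versus SMA+P2P does not follow from its own inputs

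*Combined protocol and SAP*

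**What the plan says.** Section 5.6.2 sets the target as a "clinically meaningful decline in A1c of 0.5% or a SBP decline of 5mm Hg between SMA and SMA+P2P". For the spread it says "The standard deviation of a decline in A1c was estimated to be 1.45", and for clustering "Thus we used a range of 0 to 0.10 for the estimate of ICC". On the number and size of groups it says "We estimate that we can conduct 10 to 16 SMA groups per site (equally distributed between SMA and SMA+P2P) with 8-14 people per group".

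The next sentence gives the power result. At the low estimate of 10 groups per site, a 0.5% difference in A1c is detectable with power 0.8 "for all but the lowest number of participants per group (10) and highest ICC (0.1"). The method named is Satterthwaite's approximate F test. No alpha is given.

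The number of sites appears in several forms:
- The opening of section 5.6.2 counts five health systems, which it equates with 8 sites because one system runs the program in four places.
- Later in 5.6.2, the active-treatment total is put at 560 to 1,568. Table 5 has seven rows.
- Section 5.1.1 says "This project is being conducted at five VA facilities (including eight clinics) implementing SMAs as part of usual care".
- Elsewhere, including section 5.1.1 and Aim 3, the protocol speaks of five sites.

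Group size also varies. Section 5.6.2 has 8-14. Section 5.2, under Data Pull, says "A full group will range from 10" and continues to 14.

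**The concern.** The group-size conflict is visible without calculation: one sentence sets the minimum at 8 and the next calls 10 the lowest. The site conflict appears once the power figures are recomputed. With eight sites, or with the seven that the totals imply, no combination of group size and ICC in the stated ranges falls below 0.8, so the printed exception should not exist.

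This is the only A1c power result for the comparison of the two active arms. Section 5.1.1 calls that comparison the first analysis, and it is the one protected by the random sequence of groups within site. A reader cannot tell from the text whether worst-case power is 0.74 or 0.91. That matters if the two-arm result is reported, and equally if it is set aside for insufficient numbers, because the planned precision is the reference for either decision.

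**Working it through.** **Inputs (section 5.6.2).** Difference d = 0.5. SD = 1.45. ICC ρ from 0 to 0.10. Low estimate of 10 groups per site split equally, so 5 groups per arm per site and k = 5 × sites. Group size m from 8 to 14. Two-sided alpha of 0.05 is my assumption. No allowance for missing outcomes, as in the plan's calculation.

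**Formula.** Variance of the difference V = 2·SD²·[1 + (m−1)ρ]/(k·m). Noncentrality = d/√V. Power comes from the noncentral t with 2(k−1) degrees of freedom, which is what the Satterthwaite test reduces to when both arms have the same clustering and size.

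**Reproducing the printed exception.** Five sites, k = 25, m = 10, ρ = 0.10:
- V = 2 × 2.1025 × 1.9/250 = 0.03196
- noncentrality = 0.5/0.1788 = 2.797, df = 48, power = 0.782

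At m = 12 the power is 0.815, and at m = 14 it is 0.838. At m = 11 it is 0.800 to three decimals, on the boundary. At ρ = 0.05 and m = 10 it is 0.880. So with five sites and groups of 10 or more, 10 per group at ICC 0.10 is the one cell clearly below 0.8, which is the pattern the plan prints. A normal approximation gives the same picture (0.799 at 10, 0.816 at 11).

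**The other site counts, m = 8, ρ = 0.10** (numerator 2 × 2.1025 × 1.7 = 7.1485):
- Five sites: V = 7.1485/200 = 0.03574, noncentrality 2.645, power 0.736
- Seven sites: V = 7.1485/280 = 0.02553, noncentrality 3.129, power 0.870
- Eight sites: V = 7.1485/320 = 0.02234, noncentrality 3.345, power 0.911

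**Power at ICC 0.10**

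| Sites (groups per arm) | m = 8 | m = 9 | m = 10 | m = 12 | m = 14 |
|---|---|---|---|---|---|
| 5 (25) | 0.736 | 0.762 | 0.782 | 0.815 | 0.838 |
| 7 (35) | 0.870 | 0.889 | 0.904 | 0.925 | 0.939 |
| 8 (40) | 0.911 | 0.926 | 0.937 | 0.954 | 0.964 |

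ICC 0.10 is the worst case, so with seven or eight sites nothing falls below 0.8. With five sites and the stated minimum of 8, the shortfall covers 8, 9 and 10 per group. At ICC 0.05 the five-site value at 8 per group is already 0.828.

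**Enrolment totals.** Minimum = sites × 10 × 8; maximum = sites × 16 × 14.
- Five sites: 400 and 1,120
- Seven sites: 560 and 1,568 (the printed figures)
- Eight sites: 640 and 1,792

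**Dependence on alpha (ICC 0.10).**
- One-sided 0.05, five sites: 0.832 at 8 and 0.867 at 10, so no exception.
- Two-sided 0.025, seven sites: one failing cell, but at 8 per group (0.797), not 10.
- Two-sided 0.025, six sites: 0.775 at 10 and 0.811 at 12, which resembles the printed pattern, but six sites appears nowhere in the documents.
- Two-sided 0.01, seven sites, groups of 10, 12 and 14: a normal approximation leaves only 10 per group short (0.768). With the t reference, 12 per group also fails (0.785).

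**The case against.** The strongest reply is that the error is mostly harmless. With seven or eight sites the sentence is conservative, since true power is 0.87 or better. With five sites the plan already admits the miss at 10 per group, so only 8 and 9 per group are undisclosed, and at an ICC that the plan treats as an upper limit and found not significantly different from zero. The current primary analysis in section 5.6.1 compares everyone scheduled for an SMA with usual care and has its own power statement. The same section says the two-arm comparison may be dropped because few patients took up peer pairing. All of this stands, and it limits the consequence. It does not make the printed statement follow from the section's inputs.

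Two stronger readings are tempting and are not supported:
- A reader might infer that the power statement describes a design the trial does not have. Both hidden values are in the documents. The protocol often uses site for the five facilities, the cap of 1,100 active patients in section 5.1.3 is close to the five-site maximum of 1,120, and section 5.2 gives full groups as 10-14. The defect is that section 5.6.2 does not keep to one meaning of site or one range.
- A reader might infer that five sites is the only possible source, or that the trial is underpowered. The first depends on an alpha the plan does not state. The second holds only at ICC 0.10, with five sites and groups of 10 or fewer.

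The count of seven is also an inference. It comes from factoring the totals and from the rows of Table 5; the text never says seven sites.

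**Conclusion.** The point holds as a defect of consistency and reproducibility in a stated power figure. Section 5.6.2 uses 8 sites in its text, 7 by implication in its totals and, most plausibly, 5 in its A1c power sentence. It also gives two different minimum group sizes in consecutive sentences. Depending on the site count, power at ICC 0.10 and 8 per group runs from 0.74 to 0.91, and at 10 per group from 0.78 to 0.94. The attribution to five sites rests on two-sided alpha 0.05 and on considering only site counts found in the documents. The group-size contradiction and the mismatch between 8 sites and the totals need no assumption about alpha. Nothing here shows that the primary comparison with usual care lacks power.

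**What to change.** In section 5.6.2:
1. State alpha and whether the test is one- or two-sided.
2. Define site once, as facility or as clinic, and give one count.
3. Use one group-size range, and reconcile it with the full-group range in section 5.2.
4. Replace the A1c power sentence with a grid for that site count, group sizes 8 to 14 and ICC 0 to 0.10. At two-sided 0.05, eight sites would support a minimum of 0.91 and seven a minimum of 0.87. If site means the five facilities, the grid should show 0.74, 0.76 and 0.78 at 8, 9 and 10 per group with ICC 0.10.
5. Recompute the enrolment totals on the same basis, and carry the minimum through to section 5.2, which repeats 560.

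A row allowing for missing outcomes is optional. The earlier P2P trial's 89% completion (section 2.6) suggests 11% loss. That is a different trial with its own follow-up, so the figure must be labelled an assumption. Applying it to m at ICC 0.10 and 8 per group gives 0.709, 0.848 and 0.893 for five, seven and eight sites.

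The cost is one rerun of the calculation and a few lines of text. No extra patients are needed.

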## **4.0 Resources and Personnel**

### **4.1 Where Research will be Conducted**

The study will be based at the VA HSR&D Center for Clinical Management Research (Ann Arbor Health Care System). This site has extensive expertise conducting VA and other federally-funded research and has the resources necessary to carry out the proposed research project. The Ann Arbor study team will be responsible for hosting the servers where the study data are stored, and for granting permissions as required for the conduct of this study. All employee participants will be recruited for interviews by Ann Arbor study staff. Patient participants who have been selected for telephone interviews and who have given verbal consent when contacted by a RC from their site will be contacted and interviewed by Ann Arbor study staff by telephone.

Patient participants will be recruited from five VA Medical Centers: Ann Arbor, West Haven, Palo Alto, Sacramento, and Providence. The Palo Alto site will include four locations: Palo Alto, Monterey, San Jose, and Livermore clinics.

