#### **5.1.3 Study Population**

##### **VA Patients**

We will enroll up to 1,100 VA patients to the SMA and SMA+P2P groups and 1,100 VA patients to the control group. Inclusion criteria are reflective of the criteria to participate in SMAs and P2P, with the addition of criteria to insure informed consent. Please see section 5.4 for a complete list of these criteria.

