## **5.2 Recruitment Methods**

At a minimum, we will require 560 VA patients in the SMA and SMA+P2P groups and 560 VA patients in the control group (see power calculation in Section 5.6.1 below). We will also enroll up to 56 VA employees.

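### Section 5.6.2 states eight sites, but its 560 to 1,568 active patients is the seven-site product; its upper figure exceeds the 1,100 limit in 5.1.3, and its lowest group size is both 8 and 10

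*Combined protocol and SAP*

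**What the plan says.** All places are in the combined protocol and SAP.

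- **Sites.** Section 5.6.2 opens with "We chose five VA health systems (8 sites, as one healthy system will implement the program in 4 separate sites within the system". Section 5.1.1 agrees: "This project is being conducted at five VA facilities (including eight clinics) implementing SMAs as part of usual care". Section 4.1 lists five medical centres and adds "The Palo Alto site will include four locations: Palo Alto, Monterey, San Jose, and Livermore clinics", which makes 4 + 4 = 8 locations.
- **Groups.** Section 5.6.2 twice gives 10 to 16 SMA groups per site, split equally between the two active arms, with 8 to 14 people in each.
- **Resulting range.** The same section says "At the minimum, this would give us 560 people in active treatment and an equal number of inactive controls", gives 1,568 as the corresponding maximum, and then commits to it: "Across all sites, we will recruit between 560 and 1,568 active treatment patients and an equal number of inactive controls".
- **Required minimum.** Section 5.2 says "At a minimum, we will require 560 VA patients in the SMA and SMA+P2P groups and 560 VA patients in the control group" and points to the power calculation.
- **Upper limit.** Section 5.1.3 says "We will enroll up to 1,100 VA patients to the SMA and SMA+P2P groups and 1,100 VA patients to the control group".
- **Lowest group size.** In 5.6.2, the sentence straight after the 8 to 14 range claims power of 0.8 for a 0.5% A1c difference between SMA and SMA+P2P. It excepts only the smallest group size at the highest ICC (0.1), and puts that smallest size at 10.

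**The concern.** The total should be the product of three stated inputs, and it is not. The recruitment section relies on the lower end as a required minimum, so a reader should be able to derive it from the design described.

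The upper end bears on how many people may be entered. Section 5.1.3 and section 5.6.2 both state a limit, and they differ. This matters most for the controls, whose records are to be drawn under a requested waiver of informed consent and HIPAA authorization (section 5.1.1), so the permitted number should be clear.

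The group-size conflict means that the power sentence for SMA against SMA+P2P does not cover the smallest groups in the plan, which are the groups behind 560.

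**Working it through.** **1. Range of active patients.** N = sites × groups per site × people per group, with 10 to 16 groups and 8 to 14 people (section 5.6.2).

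| Sites | Minimum | Maximum | Matches 560 and 1,568? |
|---|---|---|---|
| 7 | 7 × 10 × 8 = 560 | 7 × 16 × 14 = 1,568 | yes, both ends |
| 8 (stated) | 8 × 10 × 8 = 640 | 8 × 16 × 14 = 1,792 | no |
| 5 (health systems) | 5 × 10 × 8 = 400 | 5 × 16 × 14 = 1,120 | no |

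The ratio of the stated ends, 1,568 / 560 = 2.8, equals (16 × 14) / (10 × 8) = 224 / 80 = 2.8. The group inputs were therefore used as stated, and the site multiplier is what differs. The shortfall against eight sites is 640 − 560 = 80 at the bottom and 1,792 − 1,568 = 224 at the top, 12.5% at each end. Table 5 has seven rows and none for San Jose, which fits a count of seven.

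**2. Upper limit.** 1,568 − 1,100 = 468, for active patients and again for controls. With eight sites the gap would be 1,792 − 1,100 = 692. The minimum of 560 lies below the limit and does not conflict with it.

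**3. Lowest group size.** 560 requires m = 8 people per group. The A1c sentence takes its lowest m as 10, so m = 8 lies outside what it describes.

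**4. Does 560 + 560 support the comparison with usual care?** Inputs from 5.6.2: A1c difference 0.5 with SD 1.45; SBP difference 5 mmHg with 17 mmHg; ICC 0.10 in the SMA arm and 0 in controls. The plan calls the 17 mmHg a standard error; I take it as the person-level SD of change. Two-sided alpha 0.05 is my assumption, because the plan states none. I take n = 560 per group, with 70 SMA groups of 8.

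- Design effect in the SMA arm: 1 + (8 − 1) × 0.10 = 1.7.
- Standard error of the difference: SD × √(1.7/560 + 1/560). A1c: 1.45 × √(2.7/560) = 0.1007. SBP: 17 × √(2.7/560) = 1.180.
- Satterthwaite df ≈ 167.
- Noncentrality: A1c 0.5 / 0.1007 = 4.97; SBP 5 / 1.180 = 4.24.
- Power from the noncentral t: A1c 0.999, SBP 0.988.

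The plan's claim of at least 0.8 for this comparison holds at its stated minimum.

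**5. The A1c sentence, SMA against SMA+P2P.** There are 10 groups per site, so k = 5 × sites groups per arm. The standard error is 1.45 × √(2 × (1 + (m − 1) × ICC) / (k × m)), with df = 2(k − 1). At ICC 0.10, power is:

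| Sites | Assumed two-sided alpha | m = 8 | m = 10 |
|---|---|---|---|
| 7 | 0.05 | 0.870 | 0.904 |
| 8 | 0.05 | 0.911 | 0.938 |
| 7 | 0.025 | 0.797 | 0.843 |
| 8 | 0.025 | 0.853 | 0.892 |

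In the row for 7 sites and alpha 0.025, only the smallest group falls below 0.8. The sentence would then be right apart from giving the smallest size as 10. At alpha 0.05 no exception arises at 7 or 8 sites. The plan gives neither the alpha nor the site count behind the sentence, so it cannot be checked as written.

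**The case against.** The best defence is that nothing depends on this. Section 5.6.2 already supports 560 + 560 on power, claiming 0.8 for both outcomes against controls, and step 4 confirms the claim. Section 5.6.1 makes the comparison with usual care primary and warns that SMA against SMA+P2P may not be analysed. That stands, and it limits the point to stated figures.

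The gap at the upper end might also be a difference in what is counted: people in groups in 5.6.2 and enrolled participants in 5.1.3, since patients may attend SMAs without joining the study. That could explain part of it for active patients, though the plan does not say so. It cannot explain the controls, who attend no groups.

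Three stronger readings are tempting, and the documents do not support them:

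- **That section 5.2 contradicts the range of 8 to 14.** It says "A full group will range from 10 – 14 patients depending upon the site resources". That describes when a group is filled. The planning range in 5.6.2 can include underfilled groups, and the full-group size is not an input to its product.
- **That the A1c power exception is wrong, or reveals a third site count.** Both inferences depend on an alpha that the plan does not give. Five sites at alpha 0.05 give 0.782 at 10 per group and 0.815 at 12, which would fit the sentence, but so would other inputs.
- **That the missing San Jose row is itself an error.** Table 5 is described as a snapshot, and tables may have been damaged in extraction. The row is supporting evidence only.

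**Conclusion.** The point holds as an inconsistency in the sample-size figures. The stated eight sites give 640 to 1,792 active patients, while the printed 560 to 1,568 belongs to seven. This is plain arithmetic and rests on no assumption. The upper limits in 5.1.3 and 5.6.2 differ by 468 in each group; for the controls the plan offers no explanation. The lowest group size is given as both 8 and 10 in consecutive sentences of 5.6.2, so the A1c sentence for SMA against SMA+P2P leaves out the group size that produces 560.

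A reader might infer that the trial is underpowered or that 560 + 560 is unsupported. Neither follows. Under the assumptions in step 4, the comparison with usual care has power of about 0.999 for A1c and 0.988 for SBP at that size, so the primary comparison is unaffected.

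**What to change.** 1. Use one site count throughout 5.6.2. Either restate the range as 640 to 1,792 for eight sites, or state that seven sites are counted and keep 560 to 1,568.
2. Make the upper limits in 5.1.3 and 5.6.2 agree, for active patients and for controls, and say whether the active figure counts group attendees or enrolled participants.
3. In the A1c sentence for SMA against SMA+P2P, correct the lowest group size to match the range of 8 to 14, and state the alpha and site count behind it.
4. The 560 + 560 minimum in 5.2 can stay as a power-based minimum, whichever site count is chosen.

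The cost is wording and stating two inputs that the existing calculation must already have used. No extra patients are needed.
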